### 2.3 BENEFIT - RISK ASSESSMENT

Participation in this study is without any (therapeutic) benefit for healthy subjects. Their participation in the study, however, is of major importance to the development of tablet formulation of DE. The subjects are exposed to the risks of the study procedures and the risks related to the exposure to the trial medication.

#### Procedure-related risks

The use of an indwelling venous catheter for the purpose of blood sampling may be accompanied by mild bruising and also, in rare cases, by transient inflammation of the wall of the vein. In addition, in rare cases a nerve might be injured while inserting the venous

Proprietary confidential information © 2017 Boehringer Ingelheim International GmbH or one or more of its affiliated companies

catheter, potentially resulting in paresthesia, reduced sensibility, and/or pain for an indefinite period. The same risks apply to veinipuncture for blood sampling.

The total volume of blood withdrawn during the entire study per subject will be around 160 mL. No health-related risk to healthy subjects is expected from this blood withdrawal.

The use of an indwelling glass microelectrode in the stomach for the purpose of intragastric pH examination may be accompanied by nausea, epistaxis, sore throat and also, the accidental breathing in of gastric acid into the lungs while inserting a glass microelectrode. In addition, in rare cases shock or symptoms of toxicosis might be caused by local aesthesis while inserting the glass microelectrode.

#### Drug-related risks and safety measures

The most significant potential risk associated with DE is a minor bleeding tendency at doses higher than 600 mg per day during steady state in healthy volunteers [[U00-1856](#)]. For Japanese healthy volunteers, bleeding event was observed after treatment with a single dose of 300 mg. For details of AEs in Japanese subjects included in phase I trials, see the [Section 1.2](#).

In Japan, DE has market authorisation with the dose regimen of 150 mg b.i.d. (reduction to 110 mg b.i.d. should be considered for the patients aged 70 and older, with moderate renal failure [CrCl 30-50 mL/min], or with history of gastrointestinal haemorrhages, or those who are receiving P-gp inhibitors). The risks to the subjects are low after a single dose of 110 mg which is the dosage selected for the present study. Regardless of the low bleeding risk and the overall good tolerability of the available formulations of DE, subject's safety will be ensured by the monitoring of subjects for both expected and unexpected AEs clinically, verbally, and by laboratory monitoring.

#### Rabeprazole

Rabeprazole and DE have different metabolic pathways. The main metabolic pathway of rabeprazole is non-enzymatic reduction reaction in plasma and via CYP2C19, while DE is converted to dabigatran by esterase catalysed hydrolysis. In addition, there are no overlap in their safety profiles [[R17-0224](#), [c01632884-04](#)]. Thus, it is not expected to increase severity or frequency of AE of DE and rabeprazole by co-administration.

There are no trials which investigated the effect of co-administration of DE with rabeprazole. However, there are 6 trials that examined the effect of co-administrations of capsule formulation of DE with pantoprazole (PPI), which has similar metabolic profile with rabeprazole, to healthy subjects. Most of those trials did not cause any AEs which were considered as study drug related. Two trials experienced the study drug related AEs, gingiva bleeding, flatulence and hematoma. However, those were all of mild intensity and recovered without any therapies. There were no unexpected AEs in those trials. Further, all events were expected as side effect of DE and PPI. In addition, AEs which were considered as not study drug related were mostly accidental events (e.g., common cold), which were diagnosed as mild to moderate [[U03-1878](#), [U00-1855](#), [U01-1665](#), [U02-1100](#), [U02-1451](#), [U02-1611](#), [U03-1069](#), [U03-1353](#)].

Proprietary confidential information © 2017 Boehringer Ingelheim International GmbH or one or more of its affiliated companies

Based upon the above information, healthy subjects will not be exposed to undue risks from this trial. However, subject's safety will be ensured carefully by the clinical observation, and by laboratory monitoring.

Proprietary confidential information © 2017 Boehringer Ingelheim International GmbH or one or more of its affiliated companies

### 3. DESCRIPTION OF DESIGN AND TRIAL POPULATION

#### 3.1 OVERALL TRIAL DESIGN AND PLAN

The study will be performed as an open-label, single-oral-dose, two-period, single-arm trial in healthy male subjects in order to compare BA of DE with and without rabeprazole. The subjects will be allocated to a treatment sequence, DE without rabeprazole and then DE with rabeprazole. To make sure to increase intragastric pH, 20 mg of rabeprazole will be administrated once daily on Day -4 to -1 of Visit 3 (pre-medication). Pre-medication of rabeprazole starts at the following day of Day 3 of Visit 2. The treatments will be a single dose of 110 mg of DE with or without rabeprazole in a fasting state on Day 1 in both Visit 2 and Visit 3. For details refer to [Section 4.1](#).

[figure not shown]

Figure 3.1: 1

Trial Design

There will be a period of 6 days between administrations of DE. At least 4 days of washout are required in consideration of the period when measurable drug levels effects are still likely to be present. The interval of DE administrations satisfies this requirement.

An overview of all relevant trial activities is provided in the [Flow Chart](#). For visit schedule and details of trial procedures at selected visits, refer to [Sections 6.1](#) and [6.2](#), respectively.

#### 3.1.1 Administrative structure of the trial

The trial is sponsored by BI.

Nippon Boehringer Ingelheim Co., Ltd. (NBI) has appointed a Trial Clinical Monitor, responsible for coordinating all required activities, in order to

- manage the trial in accordance with applicable regulations and internal SOPs,
- direct the clinical trial team in the preparation, conduct, and reporting of the trial,
- ensure appropriate training and information of local clinical monitors (CML), Clinical Research Associates (CRAs), and participating trial sites.

The trial medication will be provided by the Clinical Trial Supplies Unit (CTSU), BI, Biberach, Germany and NBI.

Proprietary confidential information © 2017 Boehringer Ingelheim International GmbH or one or more of its affiliated companies

The trial will be conducted a [REDACTED] under the supervision of the Principal I

Safety laboratory tests will be performed by the local laboratory of the trial site [REDACTED]

The analyses of free, nonconjugated dabigatran and of total dabigatran concentrations in plasma will be performed at the contract research organisation [REDACTED]

On-site monitoring will be performed by NBI.

Data management and statistical evaluation will be done by NBI or a contract research organisation appointed by NBI according to BI SOPs.

Tasks and functions assigned in order to organise, manage, and evaluate the trial are defined according to BI SOPs. A list of responsible persons and relevant local information can be found in the Investigator site file (ISF).

### **3.2 DISCUSSION OF TRIAL DESIGN, INCLUDING THE CHOICE OF CONTROL GROUP**

A fixed sequence design was selected to avoid long-term burden of being hospitalised healthy volunteers although potential sequence-effects would be included in treatment effects. The fixed-sequence design is not expected to lead to systematic errors in the estimation of the treatment effects, because the trial duration is short enough to eliminate nonspecific time-effects.

Blinding is not necessary. The open-label treatment is not expected to bias results, since the study endpoints are derived from measurement of plasma concentration of the analyte provided by a bioanalytical laboratory which is blinded to the treatment sequence.

### **3.3 SELECTION OF TRIAL POPULATION**

It is planned that 36 healthy male subjects will enter the study. They will be recruited from the volunteers' pool of the trial site.

A log of all subjects enrolled into the trial (i.e., having given informed consent) will be maintained in the ISF at the investigational site irrespective of whether they have been treated with investigational drug or not.

#### **3.3.1 Main diagnosis for study entry**

The study will be performed in healthy subjects.

#### **3.3.2 Inclusion criteria**

Subjects will only be included into the trial, if they meet the following criteria:

Proprietary confidential information © 2017 Boehringer Ingelheim International GmbH or one or more of its affiliated companies

1. Healthy male subjects according to the investigator's assessment, based on a complete medical history including a physical examination, vital signs (blood pressure [BP], pulse rate [PR]), 12-lead electrocardiogram (ECG), and clinical laboratory tests
2. Age  $\geq 20$  and  $\leq 40$  years at informed consent
3. Body mass index (BMI) of  $18 \geq$  and  $\leq 25 \text{ kg/m}^2$  at screening
4. Signed and dated written informed consent prior to admission to the study in accordance with Good Clinical Practice (GCP) and local legislation

### **3.3.3 Exclusion criteria**

Subjects will not be allowed to participate if any of the following general criteria apply:

1. Any finding in the medical examination (including BP, PR or ECG) is deviating from normal and judged as clinically relevant by the investigator
2. Measurement of systolic BP outside the range of 90 to 140 mmHg, diastolic blood pressure outside the range of 50 to 90 mmHg, or PR outside the range of 45 to 90 bpm at screening
3. Any laboratory value outside the reference range before administration of DE that the investigator considers to be of clinical relevance
4. Any evidence of a concomitant disease judged as clinically relevant by the investigator
5. Any relevant bleeding history considered by the investigator
6. Any history or evidence of blood dyscrasia, haemorrhagic diathesis, severe thrombocytopenia, cerebrovascular haemorrhage, bleeding tendencies associated with active ulceration or overt bleeding of gastrointestinal, respiratory or genitourinary tract or any disease or condition with haemorrhagic tendencies
7. Gastrointestinal, hepatic, renal, respiratory, cardiovascular, metabolic, immunological or hormonal disorders
8. Any history of hypochlorhydria or achlorhydria
9. Cholecystectomy and/or surgery of the gastrointestinal tract that could interfere with the pharmacokinetics of the trial medication (except appendectomy and simple hernia repair)
10. Planned surgeries within four weeks following the end-of trial examination
11. Diseases of the central nervous system (including but not limited to any kind of seizures or stroke), and other relevant neurological or psychiatric disorders
12. History of relevant orthostatic hypotension, fainting spells, or blackouts

Proprietary confidential information © 2017 Boehringer Ingelheim International GmbH or one or more of its affiliated companies

13. Chronic or relevant acute infections
14. History of relevant allergy or hypersensitivity (including allergy to the trial medication or its excipients)
15. Use of drugs within 30 days prior to administration of trial medication if that might reasonably influence the results of the trial (incl. QT/QTc interval prolongation)
16. Participation in another trial where an investigational drug has been administered within 60 days prior to planned administration of trial medication, or current participation in another trial involving administration of investigational drug
17. Smoker (more than 10 cigarettes or 3 cigars or 3 pipes per day)
18. Inability to refrain from smoking at trial site
19. Alcohol abuse (consumption of more than 30 g per day: e.g., 750 ml of beer, 1.5 *gous* [equivalent to 270 mL] of *Sake*)
20. Drug abuse or positive drug screening
21. Blood donation of more than 100 mL within 30 days prior to administration of trial medication or intended donation during the trial
22. Intention to perform excessive physical activities within one week prior to administration of trial medication or during the trial
23. Inability to comply with dietary regimen of trial site
24. Subject is assessed as unsuitable for inclusion by the investigator, for instance, because considered not able to understand and comply with study requirements, or has a condition that would not allow safe participation in the study

For study restrictions, refer to [Section 4.2.2](#).

### **3.3.4 Removal of subjects from therapy or assessments**

#### **3.3.4.1 Removal of individual subjects**

An individual subject is to be removed from the trial if:

1. The subject withdraws consent for trial treatment or trial participation, without the need to justify the decision
2. The subject needs to take concomitant drugs that interfere with the investigational product or other trial medication

Proprietary confidential information © 2017 Boehringer Ingelheim International GmbH or one or more of its affiliated companies

3. The subject is no longer able to participate for other medical reasons (such as surgery, AEs, or diseases)
4. An AE or clinically significant laboratory change or abnormality occurred that is considered by the investigator to warrant discontinuation of treatment.
5. Clinical evidence of prolongation of coagulation, i.e., prolonged bleeding at the venipuncture site (defined as >15-minute compression necessary)
6. Sustained minor bleedings which cannot be controlled by local haemostasis, or any other bleeding event considered clinically relevant by the investigator.

A subject can also be removed from the trial if eligibility criteria are being violated or if the subject fails to comply with the protocol (for instance, by non-adherence to dietary rules, or non-attendance at study assessments).

If a subject is removed from or withdraws from the trial prior to first administration of trial medication, the data of this subject will not be entered in the case report form (CRF) or trial database and will not be reported in the clinical trial report (CTR). If a subject is removed from or withdraws from the trial after first administration of trial medication, this will be documented and the reason for discontinuation must be recorded in the CRF. In this case, the data will be included in the CRF/trial database and will be reported in the CTR. At the time of discontinuation a complete end of trial examination will be performed if possible and the information will be recorded in the CRFs. If the discontinuation occurs before the end of the residual effect period (REP) (see [Section 5.2.2.2](#)), the discontinued subject should if possible be questioned for AEs and concomitant therapies at or after the end of the REP in order to ascertain collection of AEs and concomitant therapies throughout the REP, if not contrary to any consent withdrawal of the subject. These discontinuations will be discussed in the CTR.

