## FLOW CHART

Period	Visit	Day	Planned time (relative to first drug administration [h:min])	Approximate clock time of actual day [h:min]	Event and comment	Safety laboratory 	PK blood	12-lead ECG	Vital signs (BP, PR)	Questioning for AEs and concomitant therapy 
SCR	1	Within 28 days before first DE administration			Screening (SCR) 	X		X	X	
1/2	2/3	-4 	-100:00	06:00	Rabeprazole administration (Visit 3 only)					
		-3	-76:00	06:00	Rabeprazole administration (Visit 3 only)					
		-2	-52:00	06:00	Rabeprazole administration (Visit 3 only)					
		-1	-28:00	06:00	Rabeprazole administration (Visit 3 only)					
		-18:00	16:00		Admission to trial site (Visit 2 only)	X				X
	1	-4:00	06:00		Rabeprazole administration (Visit 3 only) 					
		-3:00	07:00		Insert the pH sensor 					
		-1:00	09:00				X 	X 	X 	
		0:00	10:00		Drug administration (DE)					
		0:30	10:30				X			
		1:00	11:00		Pharmacogenomics sampling 		X			
		1:30	11:30				X			
		2:00	12:00		200 mL fluid intake 		X		X	
		3:00	13:00				X			
		4:00	14:00		200 mL fluid intake, thereafter lunch 		X			
		6:00	16:00				X			
		8:00	18:00				X			
		11:00	21:00		Dinner					
		12:00	22:00				X			X
	2	24:00	10:00		Breakfast 	X	X	X	X	
		36:00	22:00				X			
	3	48:00	10:00				X			X
		48:30	10:30		Discharge from trial site (Visit 3 only)					
EOT	4	5 to 14 days after Day 1 of Visit 3 			End of trial (EOT) examination 	X		X	X	X

DE: Dabigatran Etxilate, study drug

1. Subject must be informed and written informed consent obtained prior to starting any screening procedures. Screening procedures include physical examination, check of vital signs, ECG, safety laboratory (including drug screening), demographics (including determination of body height and weight, smoking status and alcohol history), relevant medical history, concomitant therapy and review of inclusion/exclusion criteria.
2. Breath alcohol test and safety laboratory. Safety laboratory to be taken and to be medically evaluated within 24 hours prior to administration of study drug. Samples for safety laboratory will be collected after the subjects have fasted for at least 10 hours except for Visit 1. Breath alcohol test will be performed at screening, 24 hours prior to administration of DE in Visit 2 and may be repeated at any time during the study.

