#### 5.2.2.2 Adverse event collection and reporting

##### **AEs collection**

Upon enrolment into a trial, the subject's baseline condition is assessed (for instance, by documentation of medical history/concomitant diagnoses), and relevant changes from baseline are noted subsequently.

[figure not shown]
Subjects will be required to report spontaneously any AEs as well as the time of onset, end, and intensity of these events. In addition, each subject will be regularly assessed by the medical staff throughout the clinical trial and whenever the investigator deems necessary. As a minimum, subjects will be questioned for AEs (and concomitant therapies) at the time points indicated in the [Flow Chart](#). Assessment will be made using non-specific questions such as 'How do you feel?'. Specific questions will be asked wherever necessary in order to more precisely describe an AE.

A careful written record of all AEs shall be kept by the investigator in charge of the trial. Records of AEs shall include data on the time of onset, end time, and intensity of the event as well as any treatment or action required for the event and its outcome.

The following must be collected and documented on the appropriate CRF(s) by the investigator:

- From signing the informed consent onwards through the residual effect period (REP), until an individual subject's end of trial:
  - All AEs (serious and non-serious).
  - The only exception to this rule are AEs (serious and non-serious) in Phase I trials in healthy volunteers, when subjects discontinue from the trial due to screening failures prior to administration of any trial medication. In these cases, the subjects' data must be collected at trial site but will not be entered in the CRF or trial database and will not be reported in the CTR.
- After the individual subject's end of trial:
  - The investigator does not need to actively monitor the subject for AEs but should only report relevant SAEs which [REDACTED] may become aware of.

Proprietary confidential information © 2017 Boehringer Ingelheim International GmbH or one or more of its affiliated companies

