6.6 HANDLING OF MISSING DATA AND OUTLIERS

Data of screened subjects, who discontinued from the trial due to screening failures prior to administration of any trial medication, will not be included in the CTR except for those with SAE which the investigator considered related to the screening procedures. The safety data of treated subjects who were withdrawn from the trial prematurely will be reported as far as available. All withdrawals will be documented and the reason for withdrawal recorded.

Handling of missing data is according to the CTP, section 7.4. Additionally, handling information of missing data is shown as follows:

- Missing data and outliers of PK data are handled according to [\(4\)](#).
- Missing or incomplete AE dates are imputed according to BI standards (see “Handling of missing and incomplete AE dates”). [\(5\)](#)

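### Protocol 3.3.4.1 keeps every subject withdrawn before first trial medication out of the CRF, database and report, while 5.2.2.2 exempts only screening failures; the two collide for a subject withdrawn after the Visit 2 pH-electrode insertion

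*Protocol*

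**What the plan says.** Protocol 3.3.4.1 sets a rule by timing alone. "If a subject is removed from or withdraws from the trial prior to first administration of trial medication", then "the data of this subject will not be entered in the case report form (CRF) or trial database", and the data are not reported in the CTR either. The rule has no limit by reason. The removal reasons in the same section include this one: "The subject is no longer able to participate for other medical reasons (such as surgery, AEs, or diseases".

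Protocol 5.2.2.2 (AEs collection) sets a rule by reason. Its CRF collection period runs "From signing the informed consent onwards through the residual effect period (REP" and on to the subject's end of trial, for serious and non-serious events alike. It names a single exception, which applies "when subjects discontinue from the trial due to screening failures prior to administration of any trial medication". For those subjects the data stay at the site.

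The Flow Chart has "Insert the pH sensor" at -3:00 on Day 1, in the block shared by Visits 2 and 3. Dabigatran etexilate (DE) follows at 0:00, and every rabeprazole row is marked for Visit 3 only. Protocol 2.3 lists nausea, epistaxis, sore throat and aspiration of gastric acid as insertion risks, and adds that "in rare cases shock or symptoms of toxicosis might be caused by local aesthesis while inserting the glass microelectrode".

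SAP 6.6 says that data of screening failures "will not be included in the CTR except for those with SAE which the investigator considered related to the screening procedures". SAP 6.2 describes the subjects in the database as those treated plus those with such an SAE.

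**The concern.** A site that withdraws a subject between electrode insertion and the first DE dose cannot obey both protocol sections. If it follows 3.3.4.1, the event and the reason for withdrawal appear neither in the database nor in the report, and under Protocol 3.3.5 the subject may be replaced. The loss would be selective, because it falls on insertion events bad enough to stop a subject before dosing. Protocol 2.3 presents electrode insertion to subjects as a risk of taking part, so the report should be able to say how many were withdrawn because of it.

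**Working it through.** No power, error rate or estimate is involved. The check is a timeline, a count and a comparison of rules.

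**Is there a pre-medication window at Visit 2?**
- Sensor insertion: -3:00 (07:00). First DE dose: 0:00 (10:00). Window = 0:00 - (-3:00) = 3 hours. Flow Chart footnote 6 calls this approximate.
- Rabeprazole starts on the day after Day 3 of Visit 2 (Protocol 3.1 and 6.2.2). DE at Visit 2 is therefore the first trial medication.
- Insertion does take place at Visit 2. The Flow Chart row is not restricted to Visit 3, Protocol 5.3.2 places insertion on the day of DE administration, and SAP 4 uses baseline gastric pH under the reference treatment, which is given at Visit 2.

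**How many insertions fall in the window?**
- Planned insertions: 36 subjects x 2 visits = 72.
- Before first trial medication: 36, and 36/72 = 50%.

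**Test case.** A subject passes screening, is admitted on Day -1 of Visit 2, has an AE at insertion and is withdrawn before DE.
- *Protocol 3.3.4.1:* he was removed before first trial medication, so nothing goes into the CRF, database or CTR.
- *Protocol 5.2.2.2:* the AE occurred after consent and he is not a screening failure, so it must be on the CRF.
- *SAP 6.6:* its exclusion covers screening failures only, so it does not exclude him. Its scope matches 5.2.2.2.
- *SAP 6.2:* he is neither treated nor a case of a screening-procedure SAE, so the description of the database omits him.
- *SAP 6.3:* the enrolled set, used for disposition, includes everyone who consented, whether treated or not. He belongs in it, but under 3.3.4.1 there would be no data to place there.

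**Is he a screening failure?** The Flow Chart puts screening at Visit 1, and footnote 1, which lists the screening procedures, does not mention the pH sensor. Protocol 4.1.2 and 6.2.2 have eligibility determined before the subject enters the treatment periods. He is therefore not a screening failure on the documents' own account.

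**A second, separate mismatch.** SAP 6.6 keeps screening failures with an SAE related to screening procedures in the report. Neither 3.3.4.1 nor 5.2.2.2 has that exception, and 5.2.2.2 exempts serious and non-serious events alike.

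**The case against.** The best reply is that screening runs up to the first dose. The intervals in SAP 6.1.1 start screening at consent and end it at Period 1 dosing. Protocol 7.3.3 and SAP 7.8.1 assign events before first intake to screening. Exclusion criterion 3 covers laboratory values up to DE, and criterion 24 is broad enough to catch a subject who has become unfit. On that reading any pre-dose drop-out might count as a screening failure, and the sections would largely agree. This does not succeed. The interval labels say where an event is tabulated, not why a subject left, and the eligibility provisions do not turn an injured, eligible, admitted subject into a screening failure. What stands is that the term is never defined.

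Several stronger readings are tempting, and the documents do not support them:
- *That SAP 6.6 is a third contradictory rule for this subject.* It excludes only screening failures, so here it agrees with 5.2.2.2.
- *That only subjects who tolerated insertion would be counted.* A subject with epistaxis or nausea who is then dosed stays in the database, as does every subject with an event at a Visit 3 insertion.
- *That the safety information disappears.* Protocol 5.2.2.2 requires the investigator to keep a written record of all AEs and to report SAEs within 24 hours, with no pre-dose exclusion in the reporting rule.
- *That a definite percentage of withdrawals would be hidden.* No rate of withdrawal at insertion is given. Protocol 2.3 calls shock and toxicosis rare.

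It is also fair to say that 5.2.2.2 is the section dedicated to AE collection, so a site might follow it. But nothing in the protocol says that it takes precedence over 3.3.4.1.

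**Conclusion.** The conflict between Protocol 3.3.4.1 and 5.2.2.2 is real and should be removed. It concerns eligible subjects withdrawn before the first DE dose. The foreseeable case is an AE at the Visit 2 electrode insertion, a step that all 36 subjects go through before any trial medication. Under 3.3.4.1 the event and the withdrawal would be missing from the database and CTR. The clearest loss is the non-serious event that leads to withdrawal, since serious ones still go to the sponsor.

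The number of subjects affected cannot be estimated from the documents and may be zero. The safety analyses are restricted to treated subjects (Protocol 7.3.3, SAP 7.8), and an undosed subject has no post-dose concentrations, so the treated set and PK results are untouched. The consequence is limited to safety and disposition reporting. The conclusion rests on screening failure meaning failure at the Visit 1 screening and eligibility step, which the Flow Chart and Protocol 4.1.2 and 6.2.2 support.

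**What to change.** - **Protocol 3.3.4.1:** limit the exclusion to screening failures, in line with 5.2.2.2 and SAP 6.6.
- **Protocol 3.3.4.1 and 5.2.2.2:** state that a subject on whom Visit 2 procedures have started is entered in the CRF and database even if no DE is given. List all his AEs, serious and non-serious, and the reason for withdrawal in the CTR as an undosed subject.
- **SAP 6.2:** extend the description of subjects in the database to include these subjects. Widening the SAE exception in SAP 6.2 and 6.6 would not be enough, because it would still miss non-serious events.
- **Separately:** reconcile the SAP 6.6 exception for screening-procedure SAEs with Protocol 3.3.4.1 and 5.2.2.2, which have none.

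The cost is wording in two protocol sections and the SAP, CRF entry for any undosed subject, and one short listing. No analysis set or PK analysis changes.
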